9.1.3 Cumulative Study Period

Cumulative Study Period starts from the first dose of study drug in the parent studies (109 and 011B) to the last day in Study 110, regardless of whether there is 1) the planned 2-week washout period per Study 011B design; or 2) a Roll-Over Gap between the previous studies (Study 109 and Study 011B) and Study 110. For subjects not enrolled in Study 110, the Cumulative Study Period will be the same as the Previous Study Period.

Treatment-Emergent Period for the Cumulative Study Period

The treatment-emergent period for the Cumulative Study Period is the period on or after the first dose of study drug in the previous studies to 28 days (inclusive) after the last dose of study drug in Study 110, or up to the last day in Study 110, whichever occurs first. For subjects not enrolled in Study 110, the treatment-emergent period for the Cumulative Study Period will be the same as that of the Previous Study Period.

Handling of the data during the gap between previous studies (Study 109 and Study 011B) and the rollover study (Study 110)

There may be a Roll-Over Gap between the previous studies and the rollover study, defined as the time period between the Week 24 Visit of Study 109 or the Week 26 Visit of Study 011B and the date prior to the Day 1 Visit of Study 110. All analyses will be performed regardless of whether there is a Roll-Over Gap between the previous studies (Study 109 and Study 011B) and Study 110.

- This affects summary of the following possibly continuing events: 1) AEs; 2) CMs; and 3) Pulmonary Exacerbation related endpoints: Pulmonary Exacerbations, Pulmonary Exacerbations requiring hospitalizations (planned and unplanned), and Pulmonary Exacerbations requiring IV antibiotics.

Events that happen during the Roll-Over Gap will be included in the Cumulative Study Period related analysis, but not necessarily in the analysis of the previous studies or the Current Study Period for Study 110. There are possible differences between results from Cumulative Study Period and combining results from previous studies and the Study 110.

- The Roll-Over Gap will not be considered in the derivation of the analysis window. The assessments will be selected per windowing rules specified for visits in Study 110 as described in Appendix D. The same set of selected records will be associated with different visit labels for different dosing periods.

9.2 Treatment Cohort Period 2

Treatment-Emergent Period for the Treatment Cohort Period 2

For Treatment Cohort Period 2 subjects, safety analysis will be based on the treatment-emergent period, which starts from the Study 110 Week 96 dose date +1, or Week 96 visit date +1,

whichever occurs later; up to 28 days (inclusive) after the last dose of this dosing period, or the last available date in Study 110 Treatment Cohort Period 2, whichever occurs first.

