Time-to-first pulmonary exacerbation will be analyzed and plotted using the Kaplan-Meier estimates. Both on-treatment event and event after treatment discontinuation will be considered. Of subjects enrolled in the Treatment Cohort of Study 110, one without a pulmonary exacerbation before withdrawal from the current study is considered censored at the time of withdrawal, and a subject without an exacerbation who completes the efficacy analysis period is considered censored at the end of the efficacy analysis period. Of subjects not enrolled in the Treatment Cohort of Study 110, one without a pulmonary exacerbation before withdrawal from the previous study is considered censored at the time of withdrawal, and one without a pulmonary exacerbation who completes the previous study is considered censored at the end of the efficacy analysis period of the previous study.

The analysis will be provided for the active dosing period based on 109FAS by treatment arms. For subjects randomized to placebo group in Study 109, time-to-first pulmonary exacerbation during the placebo-controlled period will be analyzed similarly.

Rate of Change in LCI (Subjects From Study 109 and the Study 011B Substudy Only) and ppFEV₁

Linear mixed-effects (LMM) analyses will be conducted to estimate the overall rate of change in LCI (LCI_{2.5} and LCI_{5.0}) and ppFEV₁ during the active dosing period based on IFAS. The dependent variable will be postbaseline value in LCI and postbaseline value in ppFEV₁, respectively, and the model will include treatment groups as the fixed effect, random intercept and slope for treatment duration (in years), and adjustment for previous study (Study 109 versus Study 011B), weight (<25 kg versus ≥25 kg) and ppFEV₁ severity (<90 versus ≥90), both as determined at screening in the previous study. In the analysis of rate of change in LCI, the model will further adjust for baseline LCI as a continuous variable. The rate of change will be reported as an annualized rate of change; 95% CI will also be provided. Measurements at, and after, Week 2 of the active dosing period, will be included to estimate the rate of change. Depending on the results from Study 109 and Study 011B, different starting times may be explored if the treatment plateau is not reached by the specified time.

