- LUM 200 mg q12h/IVA 250 mg q12h (subjects aged 6 through 11 years)
- LUM 400 mg q12h/IVA 250 mg q12h (subjects aged 12 years and older)

Subjects who turn 12 years of age before or on Day 1 of Study 110 will begin receiving LUM 400 mg q12h/IVA 250 mg q12h on Day 1. Subjects who turn 12 years of age after the Day 1 Visit of this rollover study will begin receiving LUM 400 mg q12h/IVA 250 mg q12h at their next scheduled visit.

Treatment Cohort Period 2 (France only)

Treatment Cohort Period 2 will be open-label and will consist of the following dose regimen:

- LUM 200 mg q12h/IVA 250 mg q12h (subjects aged 6 through 11 years)

French subjects who turn 12 years of age during Treatment Cohort Period 2 will be discontinued from the study because there is sufficient long-term safety data in this age population. It is recommended that these subjects discuss available treatment options with their treating physicians.

Observational Cohort

The following subjects from Study 109 or Study 011B who meet the study criteria (Protocol Section 9.1) and elect to enroll in Study 110 are eligible for enrollment in the Observational Cohort:

- Subjects who received at least 4 weeks of study drug in Study 109 or Study 011B and completed visits up to Week 24 of Study 109 or Week 26 of Study 011B but who are not eligible (Protocol Sections 9.1 and 9.2) for the Treatment Cohort with lumacaftor in combination with ivacaftor.
- Subjects who received at least 4 weeks of study drug in Study 109 or Study 011B (and did not prematurely discontinue study drug treatment) and completed visits up to Week 24 of Study 109 or Week 26 of Study 011B but who elect not to continue treatment with lumacaftor in combination with ivacaftor.

Subjects in the Observational Cohort will not receive study drug and will have regularly scheduled telephone calls for approximately 2 years after their last dose of study drug in Study 109 or Study 011B to assess the post-treatment safety of lumacaftor and ivacaftor combination therapy.

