9.1.1 Previous Study Period

Previous Study Period starts from the first dose date of study drug in the parent studies (109 and 011B) to up to the first dose date of study drug in Study 110, including 1) the planned 2-week washout period per Study 011B design; or 2) the Roll-Over Gap between the previous studies (Study 109 and Study 011B) and Study 110.

For the majority of the subjects, the first dose of study drug and assessments in Study 110 will happen on the same day as the Week 24 Visit in Study 109 or the Week 26 Visit in Study 011B.

For assessment performed on the first dose day in Study 110:

- If information regarding the assessment timing is available, then the assessment time will be compared to the first dose time in Study 110 to decide whether the assessment is before the first dose, concurrent with the first dose, or after the first dose.
- If information regarding assessment timing is not available, then the record will be included in the Previous Study Period if it comes from the Previous Study database, and the record will be included in the Current Study Period if it comes from the Current Study database.

Treatment-Emergent Period for the Previous Study Period

The treatment-emergent period for the Previous Study Period is the period on or after the first dose of study drug in the previous studies to 28 days after the last dose of the previous studies, or the last day of the Previous Study Period, or up to the first dose date in Study 110 (not including the first dose date in Study 110), whichever occurs first, for subjects dosed in Study 110.

For subjects not dosed in Study 110, the treatment-emergent period will be the period on or after the first dose of study drug in the previous studies to 28 days (inclusive) after the last dose of study drug in the previous studies or to the last day in the previous studies (inclusive), whichever occurs first.

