10 STATISTICAL ANALYSIS

10.1 General Considerations

In later sections, for analysis related to FAS, Safety Set, LCI Set [REDACTED] in Treatment Cohort Period 1, the population will not be limited to subjects in Treatment Cohort Period 1, regardless of the subtitle “Treatment Cohort Period 1”. The analysis will strictly follow their definitions in Section 8 of the SAP.

For subjects in the Observational Cohort, summaries will only be provided for the disposition, demographic and baseline characteristics, and SAEs. Summaries will be provided based on all enrolled subjects in the Observational Cohort.

For subjects in the Treatment Cohort Period 2, summaries will only be provided for the disposition, demographics, AEs, SAEs, LFTs, and ophthalmologic examinations analyses.

The Schedule of Assessments is provided in Appendix A.

Treatment Cohort Period 1

For Treatment Cohort Period 1, all analyses will be provided using all available data, regardless of whether subjects turned 12 years of age and subsequently switched to the higher dose with LUM 400 mg q12h/IVA 250 mg q12h.

The efficacy and safety analysis for different Study Periods will be based on different analysis set as summarized in Table 10-1.

Table 10-1 Analysis of Efficacy and Safety Based on Different Analysis Set in Different Study Periods

Period	Efficacy			Safety
Previous/Cumulative Study Period	FAS	109 FAS	LCI Set	Safety Set
Current Study Period	110 FAS	109 ROS	110 LCI Set	110 Safety Set

Continuous variables will be summarized using the following descriptive summary statistics: the number of subjects (n), mean, standard deviation (SD), standard error (SE), median, minimum value (min), and maximum value (max). Precisions of the summary for continuous variables are detailed in Table 13-4, Appendix B.

Categorical variables will be summarized using counts and percentages. Percentages will be presented to 1 decimal place.

Baseline: The baseline value of each Study Period for the Treatment Cohort Period 1 is defined as the most recent measurement (scheduled or unscheduled) before intake of the first dose of the corresponding Study Period, except if specified otherwise. These baselines are referred to as previous study baseline, current study baseline and cumulative study baseline.

- For LCI-related parameters, the values at each visit will be calculated based on the multiple replicates per the algorithm provided by the LCI central reader as detailed in Appendix C.

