The analysis of height and height-for-age Z-score will be similar to those specified for the MMRM analysis of LCI_{2.5}, with the absolute change from previous study baseline in height or height-for-age z-score, respectively, at each visit as the dependent variable; and replacing the baseline LCI_{2.5} with baseline height or height-for-age z-score of the previous studies, respectively, as a continuous covariate. Figure for height and height-for-age Z-score will be

plotted similar to absolute change in LCI_{2.5} above. Descriptive summary based on the current study baseline for P-L/I, similar to the summary of LCI_{2.5}, will be provided separately.

Absolute change from baseline in TSQM domains

For TSQM domains, the analysis will be similar to those specified for the MMRM analysis of LCI_{2.5}, with the absolute change from previous study baseline in each domain at each visit as the dependent variable; and replacing the baseline LCI_{2.5} with domain baseline of the previous studies as a continuous covariate. Descriptive summary based on the current study baseline for P-L/I, similar to the summary of LCI_{2.5}, will be provided separately.

Number of pulmonary exacerbations (109 Subjects Only)

The number of pulmonary exacerbations will be analyzed using negative binomial regression model (PROC GENMOD) with two treatment groups: L200/I-L/I based on 109 FAS including events in the Cumulative Study Period, and P-L/I based on 109 ROS including events in the Current Study Period. All pulmonary exacerbation events in each corresponding Study Period will be included.

The model will include treatment (L200/I-L/I and P-L/I), weight (<25 kg and ≥25 kg) and ppFEV₁ severity at screening of the previous study (<90 versus ≥90). The log of time spent for each Study Period (end date of the Study Period – first dose date of the corresponding Study Period +1) in patient-years will be treated as the offset in this model.

The data during the placebo-controlled period for subjects randomized to the placebo group in Study 109 will be analyzed using a similar negative binomial regression model without the treatment in the model. Note the placebo rate might be slightly different from that estimated in Study 109 final CSR analyses, which included two arms (placebo and active) instead of the placebo arm only in this model.

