The annualized (in 48 weeks) event rate of pulmonary exacerbation, defined as number of pulmonary exacerbations divided by total exposure in each study period, will be summarized and plotted using boxplot. In addition, number of events per patient-year with 95% CI from the model will be provided.

Time-to-first pulmonary exacerbation (109 Subjects Only)

Time-to-first pulmonary exacerbation will be analyzed and plotted using the estimates from Kaplan-Meier analysis (KM analysis) in two approaches:

- KM approach 1 includes two treatment groups: 1) L200/I-L/I based on 109 FAS including time-to-first event in the Cumulative Study Period; and 2) P-L/I based on 109 ROS including time-to-first event in the Current Study Period;
- KM approach 2 includes one treatment group, placebo, based on 109 FAS including time-to-first event in the Previous Study Period only.

Both on-treatment events and events after treatment discontinuation will be considered. For subjects enrolled in the Treatment Cohort Period 1 of Study 110, any subject without a pulmonary exacerbation before completion of the eligible analysis period will be considered censored at the end of the analysis period. For subjects not enrolled into the Study 110, any subject without a pulmonary exacerbation before withdrawal from Study 109 will be considered

censored at the time of withdrawal, and any subject who completes Study 109 without a pulmonary exacerbation will be considered censored at the last dose date in Study 109.

Event of having at least 1 pulmonary exacerbation (109 Subjects Only)

Number and percentage of subjects with at least one pulmonary exacerbation will be summarized for treatment groups: 1) L200/I-L/I based on 109 FAS including events in the Cumulative Study Period; and 2) P-L/I based on 109 ROS including events in the Current Study Period.

Number and percentage of subjects with at least one pulmonary exacerbation will also be summarized for Placebo based on 109 FAS including events in the Previous Study Period in a separate column.

Subjects who have no exacerbations through the end of the corresponding Study Period will be considered as having no event. A bar chart summarizing the percentage of subjects with at least one pulmonary exacerbation will be provided.

Rate of change in LCI_{2.5}, LCI_{5.0} (Subjects from LCI Set Only) and ppFEV₁

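### SAP 9.1.3 ends the Cumulative Study Period at the parent study only for children not enrolled in Study 110, so Observational Cohort children, who are enrolled but never dosed, carry off-drug telephone follow-up into the L200/I-L/I exacerbation offset

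*SAP*

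**What the plan says.** **Who is enrolled.** SAP 8 defines enrolment by signed consent or assent plus an enrolment date; dosing is not required. SAP 10.2.1 counts children enrolled in the Observational Cohort, and also children enrolled in Treatment Cohort Period 1 but never dosed. Under SAP 7.1, Observational Cohort children receive no study drug and "will have regularly scheduled telephone calls for approximately 2 years after their last dose of study drug". Protocol 13.1.1.3 and the Observational Cohort schedule (Protocol Table 3-2, SAP Table 13-3) collect only SAEs from them.

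**Which sets keep them.** SAP 8.1 and 8.2 build the FAS, 109 FAS and Safety Set on dosing in the parent studies. SAP 10.1 adds that, for analyses on the FAS and Safety Set, "the population will not be limited to subjects in Treatment Cohort Period 1", and that the Section 8 definitions are to be followed strictly.

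**The period rules.** The default in SAP 9.1.3 is "Cumulative Study Period starts from the first dose of study drug in the parent studies (109 and 011B) to the last day in Study 110". The exception is "For subjects not enrolled in Study 110, the Cumulative Study Period will be the same as the Previous Study Period". The cumulative treatment-emergent period ends at the earlier of 28 days after the last Study 110 dose and the last day in Study 110, with the same exception. SAP 9.1.1 draws the line elsewhere: "For subjects not dosed in Study 110, the treatment-emergent period will be the period on or after the first dose of study drug", capped at 28 days after the last parent-study dose or the last day in the parent study.

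**Where the period is used.** In SAP 10.3.2.2.2 the exacerbation model takes L200/I-L/I from the 109 FAS over the Cumulative Study Period, with offset "The log of time spent for each Study Period". The Kaplan-Meier rule has one branch for children in Treatment Cohort Period 1 and another that begins "For subjects not enrolled into the Study 110, any subject without a pulmonary exacerbation before withdrawal from Study 109 will be considered". Protocol 12.4.3 splits the same children differently: "Of subjects not enrolled in the Treatment Cohort of Study 110, one without a pulmonary exacerbation before withdrawal from the previous study".

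**The concern.** A child given L200/I in a parent study who then joins the Observational Cohort falls between the two halves of SAP 9.1.3: enrolled in Study 110, so outside the exception, but never dosed in it.

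Three analyses are touched:

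- **Exacerbation rate.** The child adds up to about 2 years to the L200/I-L/I offset during which exacerbations are not assessed. Events are missed by design while time accrues, so the bias is towards a lower active rate.
- **Time to first exacerbation.** No censoring branch covers the Observational Cohort.
- **Safety.** The L/I Overall column pools the Cumulative Study Period for L200/I-L/I. An SAE long after the last dose could be counted there as a serious TEAE, while exposure under SAP 10.2.4 stops at the last dose date. Numerator and denominator would then cover different time.

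Children enrolled in Period 1 but never dosed have the same gap in the 9.1.3 rules. Placebo children do not: they enter these analyses through the 109 ROS or the 110 Safety Set, both of which require a Study 110 dose.

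**Working it through.** The documents give no figure for this point. Their only design calculation, the confidence intervals in SAP Table 7-1, does not bear on it.

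**Step 1: wording side by side**

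| Place | Who is cut off at the parent study |
|---|---|
| SAP 9.1.3, period and treatment-emergent window | not enrolled in Study 110 |
| SAP 9.1.1, treatment-emergent window | not dosed in Study 110 |
| SAP 10.3.2.2.2, Kaplan-Meier | not enrolled in Study 110 |
| Protocol 12.4.3, Kaplan-Meier | not enrolled in the Treatment Cohort |

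The second and fourth rows catch an Observational Cohort child. The first and third do not.

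**Step 2: one child**

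Inputs: 24 weeks in the parent study; about 104 weeks of calls after the last dose (SAP 7.1); 1 patient-year = 48 weeks (SAP 10.1.2.1).

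- As written: (24 + 104)/48 = 2.67 patient-years.
- Ending at the parent study: 24/48 = 0.50 patient-years.
- Excess: 104/48 = 2.17 patient-years, a factor of 5.3.

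**Step 3: the group**

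Assumptions not in the documents: 100 L200/I children from Study 109; treated children followed for 24 + 96 = 120 weeks; *k* Observational Cohort children; one common event rate; no exacerbations recorded during the calls.

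- Intended time: (100 − k) × 120 + k × 24 weeks.
- Time as written: (100 − k) × 120 + k × 128 weeks.
- Understatement: 1 − intended/as written.

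| k | Intended, weeks (PY) | As written, weeks (PY) | Understatement |
|---|---|---|---|
| 3 | 11,712 (244.0) | 12,024 (250.5) | 2.6% |
| 5 | 11,520 (240.0) | 12,040 (250.8) | 4.3% |
| 10 | 11,040 (230.0) | 12,080 (251.7) | 8.6% |

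**Step 4: sensitivity**

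- *Early stoppers.* Calls run for 2 years from the last dose, so a child who stopped at Week 4 is followed to about Week 4 + 104 = 108. For k = 10: 1 − 11,040/(10,800 + 1,080) = 1 − 11,040/11,880 = 7.1%.
- *Follow-up of treated children.* At 124 weeks each, k = 5 and 10 give 4.2% and 8.4%. At an average of 72 weeks they give 7.0% and 13.4%.

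**Step 5: does changing one word suffice?**

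Replacing *enrolled* with *dosed* in 9.1.3 sends an undosed child to the Previous Study Period. SAP 9.1.1 ends that period at the first Study 110 dose, a date this child does not have. The not-dosed sentence in 9.1.1 governs only the treatment-emergent window, whereas the offset uses the end date of the Study Period. The offset therefore stays undefined until 9.1.1 also gives an end date.

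**The case against.** The best defence is that this is shorthand. SAP 9.1 says its three periods are for Treatment Cohort Period 1 subjects. The Kaplan-Meier branches read like complements, which suggests that not enrolled was meant as not in Period 1. SAP 10.1 limits Observational Cohort summaries to disposition, demographics and baseline, and SAEs, and SAP 10.4.1 gives those SAEs their own listing. Pooling off-drug follow-up was probably never intended.

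That is fair as to intent, but it does not override the rule. SAP 9.1.3 itself legislates for children outside Period 1, and SAP 10.1 requires the Section 8 sets to be followed strictly. A programmer working from the definitions would carry the period to the last call.

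Some of the defence stands and limits the point. A reader might infer:

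- *That the SAP sets a 2-year treatment-emergent window for these children.* It does not say so. One of the two dates in its rule does not exist for them, so the window is either undefined or runs to the last call.
- *That the Kaplan-Meier analysis keeps them at risk for 2 years.* The rule is silent on them.
- *That the events per 100 patient-years denominator is inflated.* It is not; exposure ends at the last dose.
- *That these are mostly children who could not tolerate the drug.* The documents give no such frequency. Discontinuation and intolerance are possible routes into the cohort, but so is simply declining further treatment.

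The consequence is also bounded. Exacerbation rate is an other secondary endpoint, its P values are nominal (SAP 10.3.2.3), and the Previous and Current Study Period safety columns are unaffected.

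**Conclusion.** The gap is real and should be closed, but it does not threaten the study's main conclusions. As written, the Cumulative Study Period of an Observational Cohort child given L200/I runs to the last day in Study 110, and the exacerbation offset follows it. The direction of the bias is known: the modelled L200/I-L/I rate is too low.

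The size is not known, because the documents give neither the number of such children nor the size of the active arm. Under the stated assumptions it is a few per cent for 3 to 5 children and 7% to 9% for 10, and larger if treated children were followed for less time. For the cumulative treatment-emergent window and the Kaplan-Meier rule, the supportable conclusion is that the plan leaves these children undefined or uncovered. The possible entry of off-drug SAEs into L/I Overall follows from that, but it cannot be sized because no SAE rate is given.

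**What to change.** 1. In both sentences of SAP 9.1.3, replace *not enrolled in Study 110* with *not dosed in Study 110*.
2. In SAP 9.1.1, add that for children not dosed in Study 110 the Previous Study Period ends on the last day in the previous study. Without this, the first change leaves the offset with no end date.
3. In the Kaplan-Meier rule of SAP 10.3.2.2.2, replace *not enrolled into the Study 110* with *not dosed in Treatment Cohort Period 1 of Study 110*. The companion branch should then also refer to dosed children, so that each child falls under only one.

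Observational Cohort SAEs that occur after the parent-study treatment-emergent window then appear only in that cohort's own listing, as SAP 10.4.1 already provides. The cost is a few sentences in the SAP and one derivation flag for dosing in Study 110. No new data are needed. The number of affected children should be reported with the exacerbation results.
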